## PROTOCOL SUMMARY

Title:	A Trial of Palliative Lattice Stereotactic Body Radiotherapy (SBRT) for Patients with Sarcoma, Thoracic, Abdominal, and Pelvic Cancers
Study Description:	Lattice SBRT will be used to deliver palliative radiotherapy to large ( $\geq 4.5$ cm) tumors for patients with soft tissue sarcomas, thoracic cancers (including esophageal), abdominal, and pelvic cancers. The safety and efficacy of this approach will be assessed.
Objectives:	
Primary Objective:
 
 
1. To evaluate the efficacy and safety of 5-fraction palliative Lattice SBRT in patients with large lesions (<math>\geq 4.5</math> cm) who are planning to undergo palliative radiotherapy. This will be assessed with the co-primary endpoints of target lesion control at 6 months and rate of treatment-related severe toxicity within 6 months.
 
 
Secondary Objectives:
 
 
1. To assess the rate of treatment-related severe toxicity within 12 months of completion of treatment (i.e. late toxicity)
 
2. To assess patient reported toxicity with PRO-CTCAE
 
3. To assess patient-reported QoL with PROMIS
 
4. To assess patient-reported pain
 
 
Exploratory Objectives:
 
 
5. To evaluate blood for immune- and tumor damage-associated response with Lattice SBRT
 

Endpoints:	
Primary:
 
 
1. Rate of local control by RECIST at 6 months
 
2. Proportion of patients with treatment-related grade 3+ CTCAE v5.0 toxicity assessed within 6 months of completion of treatment
 
 
Secondary:
 
 
1. Proportion of patients with treatment-related grade 3+ CTCAE v5.0 toxicity at 12 months.
 
2. PRO-CTCAE assessment at baseline, post-treatment, 30 days, 3 months, 6 months, and 12 months.
 
3. PROMIS physical function, global health, anxiety, and depression assessment at baseline, post-treatment, 30 days, 3 months, 6 months, and 12 months.
 
4. Numeric Pain Scale at baseline, post-treatment, 30 days, 3 months, 6 months, and 12 months.
 
 
Exploratory: Peripheral blood immune-related biomarkers.

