**Notes:**

1. Treatment is given every other day.
2. Completed at least 2 weeks prior to treatment with Lattice SBRT.
3. Every patient will be required to have 1 on-treatment visit per standard clinical practice.
4. For women of child-bearing potential only, and within 20 days prior to study entry.
5. +/- 1 week.
6. +/- 2 weeks
7. Within the past 4 months
8. Imaging will be performed per care team. CT, MRI, or PET/CT are acceptable modalities, but it is recommended that the same method be used at all imaging timepoints.
9. Follow up will take place at 90 days, 180 days, and 360 days, +/- 4 weeks.
10. PROMIS and PRO-CTCAE will be utilized at these timepoints.
11. AEs will be tracked through 360 days post treatment.
12. Peripheral blood for immune monitoring can be collected up to 2 weeks prior to first day of treatment, but no later than 1st day of treatment.
13. Peripheral blood for immune monitoring will be collected at fraction 5 only.
14. For all patients, assessments of hematologic and metabolic function will be collected no more than 1 week before treatment (including on the day of treatment), immediately after radiotherapy completion (Fraction 5), at 48-72 hours after radiotherapy completion, and 7 days (+/- 1 day) after radiotherapy completion. This must include assessments of uric acid, potassium, phosphorus, and calcium.

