## 2.0 OBJECTIVES AND ENDPOINTS

Objectives	Endpoints	Justification for Endpoints
Primary		
To evaluate the efficacy of 5-fraction palliative Lattice SBRT in patients with large lesions who are planning to undergo palliative radiotherapy ( $\geq 4.5$ cm).	Rate of target lesion local control at 6 months per RECIST 1.1	RECIST 1.1 is a standard measure of local control.
To evaluate the acute and sub-acute toxicity of 5-fraction palliative Lattice SBRT in patients with large lesions who are planning to undergo palliative radiotherapy ( $\geq 4.5$ cm).	Rate treatment-related, non-hematologic CTCAE v5.0 Grade $\geq 3$ toxicity at 6 months	SBRT to large tumors is traditionally associated with high dose to OARs, with sequelae of radiation-induced toxicities. As these patients have no effective treatment options, evaluation of the safety of this method of dose-

		escalation with SBRT is warranted. CTCAE v5.0 is a widely accepted standardized measure of treatment-related toxicity.
Secondary		
To assess pain response to Lattice SBRT	For patients that have pain, their pain level will be assessed with the pain Numeric Rating Scale (NRS)	The NRS is an 11-point scale for patient self-reporting of pain. This is selected because it is a reliable and clinically meaningful measure of pain that is extensively used in research and clinical practice.
To assess patient-reported toxicity outcomes	For patients that do not have pain, patient-reported symptom response will be assessed with PRO-CTCAE. A treatment site specific package of PRO-CTCAE measures will be defined for each treatment location (thorax, abdomen, pelvis, extremity)	PRO-CTCAE is a standardized inventory to collected patient reported symptomatic adverse events in clinical trials.
To assess patient reported quality of life outcomes	Patient reported quality of life and functional outcomes will be measured before treatment, after treatment, and at each follow up with the PROMIS Global, Physical Function, Pain Interference, Anxiety, and Depression system	This patient reported outcome inventory was selected because it is a reliable and clinically meaningful measure of patient reported toxicities and functional outcomes.
Exploratory		

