## **5.8 Definitions of Evaluability**

All patients enrolled on the study are evaluable for toxicity if they have received at least one fraction of radiation. Patients are evaluated from first receiving study treatment until 90 days after the conclusion of treatment or death. Participants who are consented but do not receive study treatment will be replaced.

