## **7.0 REGULATORY AND REPORTING REQUIREMENTS**

The entities providing oversight of safety and compliance with the protocol require reporting as outlined below. Please refer to Appendix B for definitions and Appendix C for a grid of reporting timelines.

Adverse events will be tracked from start of treatment through 360 days following the completion of radiotherapy. All adverse events must be recorded on the toxicity tracking case report form (CRF) with the exception of:

- Baseline adverse events, which shall be recorded on the medical history CRF
- AEs that do not fall under the following categories
  - Gastrointestinal
  - Hepatobiliary
  - Immune system
  - Metabolic
  - Nervous system
  - Renal and urinary
  - Respiratory
  - Skin disorders
- AEs that are grade 1

Refer to the data submission schedule in Section 9.1 for instructions on the collection of AEs in the EDC.

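### Section 5.8 ends evaluation at 90 days, contradicting the 6-month and 12-month toxicity endpoints and leaving unsettled whether later severe events count

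*Combined protocol and SAP*

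**What the plan says.** Section 5.8 opens with the entry condition for toxicity: "All patients enrolled on the study are evaluable for toxicity if they have received at least one fraction of radiation". The next sentence sets a period: "Patients are evaluated from first receiving study treatment until 90 days after the conclusion of treatment or death".

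Other parts of the document run longer:

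- **Co-primary endpoint.** The Protocol Summary gives "Proportion of patients with treatment-related grade 3+ CTCAE v5.0 toxicity assessed within 6 months of completion of treatment". The table in Section 2.0 likewise gives "toxicity at 6 months".
- **Secondary endpoint.** The Protocol Summary gives "Proportion of patients with treatment-related grade 3+ CTCAE v5.0 toxicity at 12 months", and the matching objective labels this late toxicity.
- **Assessment schedule.** Section 5.1 has patients evaluated for toxicity at 30 days and at 3, 6 and 12 months. Sections 1.6.1 and 11.1 follow them for 12 months for treatment-related toxicity. Section 5.12 lists visits at 180 and 360 days.
- **Data collection.** Section 7.0 states "Adverse events will be tracked from start of treatment through 360 days following the completion of radiotherapy", and note 11 to the Schedule of Activities agrees: "AEs will be tracked through 360 days post treatment".

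Section 11.2 names the toxicity co-primary and calls the treatment safe if the grade 3+ treatment-related rate is below 20%, but gives no time window for either. Section 11.3 says only that toxicity will be summarised descriptively.

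**The concern.** The section titled as the definition of evaluability carries a 90-day limit directly after its sentence on toxicity, while both toxicity endpoints run past day 90. No passage says which window governs the analysis. A treatment-related grade 3+ event that starts on day 120 would be recorded under Section 7.0 and would count under the Protocol Summary, yet it lies outside the period in Section 5.8.

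Two analysts could therefore report different co-primary rates from the same data, each citing the protocol. The difference has a fixed direction: a shorter window cannot add patients with events, so applying 5.8 can only move the result toward the below-20% conclusion. The 12-month endpoint would be hit hardest, because it is meant to capture late events and would have no counted time after day 90.

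**Working it through.** **1. Windows side by side**

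| Source | End of period after treatment |
|---|---|
| 5.8 | 90 days or death |
| Protocol Summary and 2.0, co-primary | 6 months (180-day visit) |
| Protocol Summary, secondary | 12 months (360-day visit) |
| 5.1, 1.6.1, 11.1, toxicity assessment | 12 months |
| 7.0 and Schedule note 11, AE tracking | 360 days |
| 11.2, toxicity co-primary and 20% criterion | not stated |

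90/180 = 0.50 and 90/360 = 0.25. The 5.8 period covers half of the co-primary window and a quarter of the late-toxicity window.

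**2. The plan's own figure.** The only sample-size calculation is for local control: 47 evaluable patients for a 95% confidence interval of ±15%, with 67 enrolled for 30% drop-out. It reproduces. The largest half-width of an exact (Clopper-Pearson) interval is 0.1510 at n = 46 and 0.1493 at n = 47, and 47/0.70 = 67.1. Toxicity has no sample-size figure of its own, and the choice of window leaves 47 and 67 unchanged.

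**3. Effect on the rate if 5.8 were applied.** Let p be the true 6-month proportion of patients with a treatment-related grade 3+ event. Let f be the share of those patients whose *first* such event starts after day 90. A patient with events both before and after day 90 is still counted, so f is a share of patients, not of events. Then

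observed rate = p × (1 − f).

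The documents do not give f, so 10%, 25% and 50% are assumed. The value p = 24% is also assumed; it lies above the 20% criterion and inside the 5–25% range that Section 11.2 cites from earlier studies.

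- f = 10%: 24% × 0.90 = 21.6%
- f = 25%: 24% × 0.75 = 18.0%
- f = 50%: 24% × 0.50 = 12.0%

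Setting p × (1 − f) = 20% gives the true rate at which the expected reading equals the criterion: 0.20/0.90 = 22.2%, 0.20/0.75 = 26.7% and 0.20/0.50 = 40%. Only true rates strictly below these values would be expected to read below 20%.

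**4. Chance of an observed rate below 20%.** With 67 treated patients this means 13 or fewer with an event (13/67 = 19.4%; 14/67 = 20.9%). Take p = 25%, the top of the plan's cited range:

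| f | p × (1 − f) | Expected patients not counted (67 × p × f) | P(13 or fewer of 67) |
|---|---|---|---|
| 0 (full 6 months) | 25.0% | 0 | 0.18 |
| 10% | 22.5% | 1.7 | 0.33 |
| 25% | 18.75% | 4.2 | 0.63 |
| 50% | 12.5% | 8.4 | 0.96 |

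These rows show how sensitive the criterion is to the window. They do not estimate what will happen in this trial.

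**The case against.** The strongest reply is that the endpoint windows are already fixed elsewhere. The Protocol Summary and Section 2.0 define the co-primary at 6 months, and the Protocol Summary defines the secondary at 12. Section 5.1 uses the same verb as 5.8, names toxicity, and runs to 12 months; Sections 1.6.1 and 11.1 agree. Nothing in Section 11 tells the analyst to restrict counts by 5.8. The 90-day sentence does not itself mention toxicity, and the entry condition before it has no time limit. It may simply be a leftover. Since events are collected to 360 days, a careful analyst could reach the intended result without any amendment.

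Much of this stands, and it limits the point. A reader might infer that 5.8 alone sets the toxicity period, so that events after day 90 are excluded. The documents do not support that: several sections set a longer period, and 5.8 states no exclusion. Nor do they support saying that half of the co-primary window and three quarters of the late window are lost. That would follow only if 5.8 overrode the endpoint definitions, and no passage says it does.

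The conflict itself remains. The sentence sits in the evaluability section, directly after the toxicity condition, and no other subject is given for it. Section 11.2, where the 20% criterion is stated, gives no toxicity window that would settle the matter.

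**Conclusion.** Wrong as written: an internal inconsistency over which severe events count. The textual mismatch is certain, since the 90-day limit cannot be squared with endpoints at 6 and 12 months. The consequence is conditional. Only if the 5.8 window were applied to the endpoints would patients with a first treatment-related grade 3+ event after day 90 go uncounted, and the rate could then only fall relative to the 20% criterion.

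The documents do not establish the size of that fall. The readings of 21.6%, 18% and 12% rest on an assumed true rate of 24% and assumed late-onset shares of 10%, 25% and 50%. They should not be taken as a forecast of bias.

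A reader might also tie this sentence to the stopping rule in Section 11.6, which counts patients with full follow-up without giving a length. Section 11.6 makes no reference to 5.8, so that omission is a separate matter and adds no weight here.

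**What to change.** - In Section 5.8, replace the 90-day limit with 360 days after the conclusion of treatment or death, which matches Section 7.0 and note 11 to the Schedule of Activities. Keep receipt of at least one fraction as the condition for being evaluable for toxicity.
- In Sections 5.8 and 11.2, state that the co-primary counts patients with onset of a treatment-related grade 3+ event through 6 months after completion of treatment, and that the secondary endpoint counts those with onset through 12 months.

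The cost is a few sentences of text. No visits, data or patients are added, and the sample size does not change. Compared with a 90-day count, the reported toxicity rate may be slightly higher.

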## **5.9 Concomitant Therapy and Supportive Care Guidelines**

Patients may not receive any concurrent systemic therapy with radiation. The interval from last receipt of systemic therapy to the initiation (or re-initiation) of systemic therapy will be at physician discretion. Supportive care will be consistent with standards for palliative radiotherapy, directed by the treating physician.

## **5.10 Women of Childbearing Potential**

Women of childbearing potential (defined as women with regular menses, women with amenorrhea, women with irregular cycles, women using a contraceptive method that precludes withdrawal bleeding, and women who have had a tubal ligation) are required to have a negative serum/urine pregnancy test within 20 days prior to the first dose of radiation.

Female and male patients (along with their female partners) are required to use two forms of acceptable contraception, including one barrier method, during participation in the study and for 6 months following the last dose of radiation.

If a patient is suspected to be pregnant, radiation should be immediately discontinued. In addition a positive urine test must be confirmed by a serum pregnancy test. If it is confirmed that the patient is not pregnant, the patient may resume therapy.

If a female patient or female partner of a male patient becomes pregnant during therapy or within 6 months after the last dose of radiation, the investigator must be notified in order to facilitate outcome follow-up.

## **5.11 Duration of Therapy**

If at any time the constraints of this protocol are considered to be detrimental to the patient's health and/or the patient no longer wishes to continue protocol therapy, the protocol therapy should be discontinued and the reason(s) for discontinuation documented in the case report forms.

In the absence of treatment delays due to adverse events, treatment may continue for a maximum of 2 weeks or until one of the following criteria applies:

- Documented and confirmed disease progression

- Death
- Adverse event(s) that, in the judgment of the investigator, may cause severe or permanent harm or which rule out continuation of study drug
- General or specific changes in the patient's condition render the patient unable to receive further treatment in the judgment of the investigator
- Suspected pregnancy
- Serious non-compliance with the study protocol
- Lost to follow-up
- Patient withdraws consent
- Investigator removes the patient from study
- The Siteman Cancer Center decides to close the study

Patients who prematurely discontinue treatment for any reason will still be followed as indicated in the study calendar.

## **5.12 Follow-up Specifications**

Patients will be followed at 14, 30, 90, 180, and 360 days after completion of radiotherapy. Patients removed from study for unacceptable adverse events will be followed until resolution or stabilization of the adverse event. Patients may be followed in-person during visits, medical records review, phone calls, office visits, and assessment of any other clinically relevant materials after completion of therapy.

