## **5.13 Lost to Follow-Up**

A participant will be considered lost to follow-up if he or she fails to return for 90 days scheduled visits and is unable to be contacted by the study team.

The following actions must be taken if the participant fails to return to clinic for a required study visit:

- The study team will attempt to contact the participant and reschedule the missed visit within 1-2 weeks and counsel the participant on the importance of maintaining the assigned visit schedule and ascertain if the participant wishes to and/or should continue in the study.
- Before a participant is deemed lost to follow-up, the investigator or designee will make every effort to regain contact with the participant (where possible, 3 telephone calls and, if necessary, a certified letter to the participant's last known mailing address). These contact attempts should be documented in the participant's medical record or study file.
- Should the participant continue to be unreachable, he or she will be considered to have withdrawn from the study with a primary reason of lost to follow-up.

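### Section 5.8 stops toxicity evaluation at 90 days, against a 6-month toxicity co-primary and 360-day AE tracking; the Section 5.12 rule for patients removed for adverse events also needs reconciling with Section 5.11

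*Combined protocol and SAP*

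**What the plan says.** **Toxicity window.** Section 5.8 first says who counts: "All patients enrolled on the study are evaluable for toxicity if they have received at least one fraction of radiation". It then says for how long: "Patients are evaluated from first receiving study treatment until 90 days after the conclusion of treatment or death".

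Other parts of the document run longer:

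- The Protocol Summary sets the toxicity co-primary as the proportion of patients with a treatment-related grade 3+ event within 6 months of completing treatment. It sets the late-toxicity secondary at 12 months. Section 2.0 also puts the toxicity endpoint at 6 months.
- Section 5.1 plans toxicity evaluations at 30 days and at 3, 6 and 12 months.
- Section 7.0 says "Adverse events will be tracked from start of treatment through 360 days following the completion of radiotherapy", and note 11 to the Schedule of Activities gives the same 360 days.

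Section 11.2 calls the treatment safe if the grade 3+ treatment-related rate is below 20%. It restates the toxicity co-primary with no time limit.

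**Patients who stop or are removed.** Section 5.11 lists reasons for ending treatment, among them harmful AEs and "Investigator removes the patient from study". It closes with "Patients who prematurely discontinue treatment for any reason will still be followed as indicated in the study calendar". Section 5.12 opens with "Patients will be followed at 14, 30, 90, 180, and 360 days after completion of radiotherapy" and continues "Patients removed from study for unacceptable adverse events will be followed until resolution or stabilization of the adverse event". It does not say whether the scheduled visits go on for those patients.

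**The concern.** A co-primary endpoint needs one observation window. Here the section that defines toxicity evaluability gives a window half as long as the endpoint it serves. Under 5.8 a first grade 3 treatment-related event on day 130 falls outside the evaluation period; under the Protocol Summary it counts. Section 11 does not settle the matter, because 11.2 gives the toxicity endpoint no window and 11.3 says only that toxicity will be summarized descriptively. The safety conclusion is a bare comparison of one proportion with 20%, so the choice of window can decide it.

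The 5.12 sentence raises a smaller question of the same kind. If it ends follow-up once the AE settles, a patient removed for toxicity may never have the 6-month scan. A patient removed for a lower-grade event may have a later first grade 3+ event missed. Such losses are linked to toxicity and incomplete treatment, so they are not random.

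**Working it through.** **1. The plan's own sample size.** Sections 11.2 and 11.4 give 47 evaluable patients for a 95% confidence interval of ±15% on local control, and 67 enrolled to allow for up to 30% drop-out. The maximum half-width of the exact (Clopper-Pearson) interval, taken as half its total width, is 15.1% at n = 46 and 14.9% at n = 47, so 47 reproduces. Inflation gives 47 / 0.70 = 67.1, in line with 67. Nothing below changes these numbers.

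**2. The windows side by side** (days after treatment)

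| Source | Toxicity window ends |
|---|---|
| Section 5.8 | 90 days |
| Protocol Summary and Section 2.0, co-primary | 6 months (about 180 days) |
| Section 5.1, last toxicity evaluation | 12 months |
| Protocol Summary, secondary | 12 months |
| Section 7.0 and Schedule note 11 | 360 days |

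The 5.8 period covers 90/180 = one half of the co-primary window and 90/360 = one quarter of the AE-tracking window.

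**3. Direction of the error.** The denominator is everyone who received at least one fraction, whichever window is used. Patients with a first event by day 90 are a subset of those with a first event by month 6. A 90-day cut can therefore only leave the numerator unchanged or reduce it.

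**4. The safety threshold.** 0.20 × 67 = 13.4. So 13/67 = 19.4% meets the criterion and 14/67 = 20.9% does not.

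**5. Illustration.** Let p be the true 6-month rate and f the share of first events that fall after day 90. A 90-day window observes X ~ Binomial(67, p(1 − f)), and the criterion is met if X ≤ 13. The documents give neither p nor f, so both are assumed. The middle value, p = 25%, is the top of the 5–25% range that Section 11.2 quotes for earlier studies. Cells show P(X ≤ 13).

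| True 6-month rate p | f = 0 (full capture) | f = 10% | f = 25% | f = 50% |
|---|---|---|---|---|
| 20% | 0.52 | 0.69 | 0.88 | 0.99 |
| 25% | 0.18 | 0.33 | 0.63 | 0.96 |
| 30% | 0.04 | 0.10 | 0.33 | 0.88 |

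At p = 25% the expected recorded rates are 0.25 × 0.90 = 22.5%, 0.25 × 0.75 = 18.8% and 0.25 × 0.50 = 12.5%. The expected number of patients missed, 67 × 0.25 × f, is 1.7, 4.2 and 8.4.

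**6. Section 5.12 against Section 5.11.** Removal by the investigator is on the 5.11 list of reasons for ending treatment, and 5.11 keeps patients who stop for any reason on the calendar. The 5.12 sentence gives patients removed for AEs an event-based end instead, unless it is read as an extra duty. Section 4.5 expects 95% to complete therapy, so early stoppers for all reasons number about 67 × 0.05 = 3.4. Taking removal for an AE to coincide with stopping treatment early, about 3 is a ceiling. Each evaluable patient is worth 1/47 = 2.1 percentage points of local control. Losing 3 of 47 widens the exact half-width from 14.9% to 15.4%.

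**The case against.** The best defence is that the endpoint definition governs. The Protocol Summary fixes the co-primary at 6 months, Section 5.1 schedules 6- and 12-month toxicity evaluations, AE tracking runs to 360 days, and Section 9.0 has the Toxicity Form completed continuously. An event on day 130 would therefore be on the case report form, and it is lost only if the analyst lets 5.8 override the endpoint. This stands as far as it goes: the defect lies in the evaluability rule, not in data collection. It does not remove the contradiction, because 5.8 is the section headed as defining evaluability and Section 11 states no window that displaces it.

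On 5.12, the sentence does not say that visits stop. It can be read as an added duty for an unresolved AE on top of the calendar, and removal from study is not the same term as discontinuing treatment. That also stands, so 5.12 is an ambiguity and not a flat contradiction.

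Four stronger readings are tempting but not supported:

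- **Follow-up ends at 90 days for everyone.** Section 5.8 concerns toxicity evaluability. Section 5.12 schedules days 180 and 360, and Section 9.0 requires the RECIST form at 6 months and 1 year, so 5.8 does not shorten local control.
- **Second events go uncounted and bias the result.** The endpoint is a proportion of patients. Someone removed for a treatment-related grade 3+ event has normally already counted.
- **The 90-day window turns a not-safe result into a safe one.** That depends on an assumed rate and an assumed late share. Section 1.7.1 reports one potentially treatment-related grade 3+ toxicity in a pilot with 15 accrued, well below the 25% used above, and a rate far below 20% would meet the criterion under either window.
- **Section 5.13 adds to the loss.** It requires repeated contact attempts before a patient is deemed lost, and 5.12 allows follow-up by medical records review. Asking for more is a preference.

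**Conclusion.** The 90-day evaluation period in 5.8 is wrong as written against the document's own endpoints and tracking period, and should be corrected. Followed literally, it biases the toxicity co-primary in one direction, downward. The amount is unknown. At an assumed true rate of 25%, late shares of 10% to 50% raise the chance of meeting the under-20% criterion from 0.18 to between 0.33 and 0.96. These figures show sensitivity and do not predict the trial's result.

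The 5.12 sentence is a secondary ambiguity. On its restrictive reading it affects at most about 3 of 67 patients, given the plan's 95% completion estimate. The effect is mainly the lost 6-month RECIST assessment, plus a possible missed first grade 3+ event in someone removed for a lower-grade one. The loss of precision is small; the reason to act is that the loss would be related to toxicity. The planned 47 evaluable and 67 enrolled are unaffected.

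**What to change.** - **Section 5.8:** replace the 90-day evaluation period with the 6-month window for the toxicity co-primary and the 360-day window for late toxicity, consistent with the Protocol Summary and Section 7.0.
- **Section 5.12:** reconcile with 5.11 by stating that following an AE to resolution or stabilization is in addition to, not instead of, the 14/30/90/180/360-day calendar.

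The cost is wording in two sections and a few more completed forms for patients who stop early. No visit, procedure or sample-size change is needed, because the calendar and the 360-day tracking already exist. The reported toxicity rate may come out slightly higher than under a literal 90-day cut.
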